9.4.10. Screening and Baseline Procedures

After the investigator or sub-investigator confirms that a subject is eligible and willing to participate in the study, study center personnel will forward the appropriate documentation to the attention of the sponsor or sponsor delegate according to the study regulatory binder.

Within 21 days before treatment administration, perform the following study procedures and tests:

- Written informed consent. The ICF must be signed and dated by the subjects before any study-specific samples are collected or study-specific procedures are initiated.
- Complete medical history, including demographics. Record disease history, including the date of initial diagnosis and list prior treatments and responses to these treatments). Document concurrent medical signs and symptoms to establish baseline conditions.
- Complete PE per the institutional standard practice, but including a skin examination, and including height and weight.
- Vital signs include resting systolic/diastolic blood pressure, resting respiration rate, resting heart rate, and body temperature. Assess vital signs after the subject has rested in a sitting or semirecumbent position for at least 3 minutes (Section 9.4.2).
- ECOG performance status assessment (Appendix 1).
- 12-lead ECG in triplicate (Section 9.4.4).
- ECHO or MUGA scan.
- Ophthalmic examination (Section 9.4.6).
- Record screening procedure-related AEs that occur before the start of study treatment and concomitant medications starting 14 days before study treatment initiation.
- Sample collection for clinical laboratory tests (hematology, coagulation, serum chemistry, and urinalysis) (Table 10).
- Serum or urine pregnancy test: for women of child-bearing potential only. Results must be negative for the subject to be eligible for enrollment into the study.
- Blood sample collection for ctDNA and blood (PBMC) sample collection for germline DNA (Section 9.2.2, Table 8).
- Archival tumor tissue (FFPE) collection (Section 9.2.2, Table 9).
- Pretreatment fresh tumor biopsy collection (optional in Phase 1 Part A and Phase 2 and mandatory in Phase 1 Part B) (Section 9.2.2, Table 9).
- CT or MRI scan (or other appropriate disease evaluation method, including tumor marker measurement, as applicable).
- Investigator's confirmation of eligibility. Perform all necessary procedures and evaluations to document that the subject meets each eligibility criterion.

- Randomize patient (Phase 1, if applicable).
- Enroll patient.

9.4.11. Treatment and Follow-up Procedures

The first day of study drug administration is C1D1. Consecutive QD oral doses of study drug will be administered (or self-administered) on Days 1 to 21 (Regimen 1) or Days 1 to 14 (Regimen 2). For details on study drug administration please refer to Section 7.1.7. Subjects should drink 1 full glass of water immediately after drug ingestion and not lay down for at least 30 minutes after drug ingestion. On scheduled visit days, subjects should wait to take the study drug until after they have checked into the study center and undergone the predose procedures. Subjects should record the time and date of each dose they self-administer in their dosing diary.

Treatment and follow-up procedures will be followed for Regimen 1 or 2, based on the regimen selected.

9.4.11.1. Cycle 1 – Week 1

Week 1 is a dosing week in both Regimen 1 and Regimen 2: consecutive QD oral doses of study treatment will be administered (or self-administered) on Days 1 to 7.

9.4.11.1.1. Cycle 1 – Week 1 – Day 1

Before administration of study treatment:

- Perform symptom-directed PE (Section 9.4.1).
- Record subject's weight.
- Record vital signs (Section 9.4.2).
- Evaluate ECOG performance status (Appendix 1).
- Perform predose 12-lead ECG in triplicate (Section 9.4.4). Note: ECG findings must meet study entry criteria before dosing.
- Record screening procedure-related AEs that occur before the start of study treatment and concomitant medications received since screening.
- Collect blood samples for hematology, coagulation, and serum chemistry laboratory tests and review results; collect urine sample for urinalysis (Table 10). Note: hematology and chemistry values must meet study entry criteria before dosing, C1D1 hematology, coagulation, serum chemistry, and urine evaluations do not need to be repeated if screening tests are done within 4 days prior to first dose of ASTX029, and these tests may be performed on the day before the visit if more convenient.
- Perform serum or urine pregnancy test for women of child-bearing potential only, and this test may be performed within 24 hours before the start of study treatment if more convenient.
- Collect predose blood sample for PK analysis (Section 9.2.1, Table 4, Table 5, Table 6, and Table 7).

- Collect predose blood sample for ctDNA (Section 9.2.2, Table 8).
- Confirm eligibility.

Subject ingests study treatment while at the clinic.

After administration of study treatment:

- Record blood pressure and heart rate 1 hour (± 30 minutes) postdose (Section 9.4.2).
- Perform 12-lead ECG in triplicate 2 hours (± 30 minutes) postdose (Section 9.4.4).
- Record AEs and concomitant medications.
- Collect blood samples for postdose PK analysis (Section 9.2.1, Table 4, Table 5, Table 6, and Table 7).
- Dispense study treatment (ASTX029), provide instruction for self-administration, and instruct subject to, on dosing days when there is a scheduled visit, refrain from ingesting the study drug until after being on-site at the study clinic and the predose study procedures have been performed.
- Provide a dosing diary to the subject and instructions for how to enter dosing information.

9.4.11.1.2. Cycle 1 – Week 1 – Day 2

Before administration of study treatment:

- Record vital signs (Section 9.4.2).
- Perform predose 12-lead ECG in triplicate (Section 9.4.4).
- Record AEs and concomitant medications.
- Collect post C1D1 dose blood sample for PK analysis (Section 9.2.1, Table 4, Table 5, Table 6, and Table 7).

Subject ingests study treatment while at the clinic.

After administration of study treatment:

• Record AEs and concomitant medications.

9.4.11.2. Cycle 1 – Week 2 – Day 8

Week 2 is a dosing week in both Regimen 1 and Regimen 2: consecutive QD oral doses of study treatment will be administered (or self-administered) on Days 8 to 14.

Before administration of study treatment (note: hematology and serum chemistry tests may be performed on the day before the visit if more convenient):

- Perform symptom-directed PE (Section 9.4.1).
- Record vital signs (Section 9.4.2).
- Evaluate ECOG performance status (Appendix 1).

- Record AEs and concomitant medications.
- Perform predose 12-lead ECG in triplicate (Section 9.4.4).
- Collect blood samples for hematology and serum chemistry laboratory tests (Table 10).

Subject ingests study treatment while at the clinic.

After administration of study treatment:

- Record AEs and concomitant medications.
- Review dosing diary to assess dosing compliance.
- Dispense study treatment (ASTX029), provide instruction for self-administration as needed, and instruct subject to, on dosing days when there is a scheduled visit, refrain from ingesting the study drug until after being are on-site at the study clinic and the predose study procedures have been performed.

9.4.11.3. Cycle 1 – Week 2 – Day 14 Regimen 2 Only

Week 2 Day 14 is the last day of dosing in Regimen 2.

For subjects receiving Regimen 2 treatment (before administration of study treatment) (note: hematology and serum chemistry tests may be performed on the day before the visit if more convenient):

- Perform symptom-directed PE (Section 9.4.1).
- Record vital signs (Section 9.4.2).
- Evaluate ECOG performance status (Appendix 1).
- Perform predose 12-lead ECG in triplicate (Section 9.4.4).
- Record AEs and concomitant medications.
- Review dosing diary to assess dosing compliance.
- Collect blood samples for hematology and serum chemistry laboratory tests (Table 10).
- Collect predose blood sample for PK analysis (Section 9.2.1, Table 5 and Table 7).

Subject ingests study treatment while at the clinic.

For subjects receiving Regimen 2 treatment (after administration of study treatment):

- Record blood pressure and heart rate 1 hour (± 30 minutes) postdose (Section 9.4.2).
- Perform 12-lead ECG in triplicate 2 hours (± 30 minutes) postdose (Section 9.4.4).
- Record AEs and concomitant medications.
- Collect postdose blood samples for PK analysis (Section 9.2.1, Table 5 and Table 7).

9.4.11.4. Cycle 1 – Week 3 – Day 15

Week 3 is a dosing week in Regimen 1 (only): consecutive QD oral doses of study treatment will be administered (or self-administered) on Days 15 to 21.

For subjects receiving Regimen 1 treatment (before administration of study treatment) (note: hematology and serum chemistry tests may be performed on the day before the visit if more convenient):

- Perform symptom-directed PE (Section 9.4.1).
- Record vital signs (Section 9.4.2).
- Evaluate ECOG performance status (Appendix 1).
- Record AEs and concomitant medications.
- Perform predose 12-lead ECG in triplicate (Section 9.4.4).
- Collect blood samples for hematology and serum chemistry laboratory tests (Table 10).

Subject receiving Regimen 1 treatment ingests study treatment while at the clinic.

After administration of study treatment for subjects receiving Regimen 1 treatment:

- Record AEs and concomitant medications.
- Review dosing diary to assess dosing compliance.
- Dispense study treatment (ASTX029), provide instruction for self-administration as needed, and instruct subject to, on dosing days when there is a scheduled visit, refrain from ingesting the study drug until after being are on-site at the study clinic and the predose study procedures have been performed.

For subjects receiving Regimen 2 treatment:

- Record vital signs (Section 9.4.2).
- Record AEs and concomitant medications.
- Perform 12-lead ECG in triplicate (Section 9.4.4).
- Collect post C1D14 dose blood sample for PK analysis (Section 9.2.1, Table 5 and Table 7).

9.4.11.5. Cycle 2 – Week 1

Week 1 is a dosing week in both Regimen 1 and Regimen 2: consecutive QD oral doses of study treatment will be administered (or self-administered) on Days 1 to 7.

9.4.11.5.1. Cycle 2 – Week 1 – Day 1

Before administration of study treatment (note: hematology, serum chemistry, coagulation, and urinalysis tests may be performed on the day before the visit and the pregnancy test may be performed within 24 hours before administration of study treatment if more convenient):

- Perform symptom-directed PE (Section 9.4.1).
- Record subject's weight.
- Record vital signs (Section 9.4.2).
- Evaluate ECOG performance status (Appendix 1).
- Perform predose 12-lead ECG in triplicate (Section 9.4.4).
- Record AEs and concomitant medications.
- Collect blood samples for hematology, coagulation, and serum chemistry laboratory tests and review results; collect urine sample for urinalysis (Table 10).
- Perform serum or urine pregnancy test for women of child-bearing potential only.
- Collect predose blood sample for ctDNA (Section 9.2.2, Table 8).

In addition, for subjects receiving Regimen 1 treatment (before administration of study treatment):

• Collect predose blood sample for PK analysis (Section 9.2.1, Table 4 and Table 6).

Subject ingests study treatment while at the clinic.

After administration of study treatment:

- Record AEs and concomitant medications.
- Dispense study treatment (ASTX029), provide instruction for self-administration as needed, and instruct subject to, on dosing days when there is a scheduled visit, refrain from ingesting the study drug until after being are on-site at the study clinic and the predose study procedures have been performed.
- Provide a dosing diary to the subject and instructions for how to enter dosing information.

In addition, for subjects receiving Regimen 1 treatment (after administration of study treatment):

- Review dosing diary to assess dosing compliance.
- Record blood pressure and heart rate 1 hour (± 30 minutes) postdose (Section 9.4.2).
- Perform 12-lead ECG in triplicate 2 hours (±30 minutes) postdose (Section 9.4.4).
- Collect postdose blood samples for PK analysis (Section 9.2.1, Table 4 and Table 6).

9.4.11.5.2. Cycle 2 – Week 1 – Day 2 Regimen 1 Only

For subjects receiving Regimen 1 treatment (Before administration of study treatment):

- Record vital signs (Section 9.4.2).
- Record AEs and concomitant medications.

For subjects in Phase 1 receiving Regimen 1 treatment (before administration of study treatment):

• Collect post C2D1 blood sample for PK analysis (Section 9.2.1, Table 4).

Subject ingests study treatment while at the clinic.

For subjects receiving Regimen 1 treatment (After administration of study treatment):

• Record AEs and concomitant medications.

9.4.11.6. Cycle 2 – Week 2 – Day 8

Week 2 is a dosing week in both Regimens 1 and 2: consecutive QD oral doses of study treatment will be administered (or self-administered) on Days 8 to 14.

Before administration of study treatment (note: hematology and serum chemistry tests may be performed on the day before the visit if more convenient):

- Perform symptom-directed PE (Section 9.4.1).
- Record vital signs (Section 9.4.2).
- Evaluate ECOG performance status (Appendix 1).
- Record AEs and concomitant medications.
- Collect blood samples for hematology and serum chemistry laboratory tests (Table 10).

Subject ingests study treatment while at the clinic.

After administration of study treatment:

- Record AEs and concomitant medications.
- Collect fresh tumor biopsy (optional in Phase 1 Part A and Phase 2 and mandatory in Phase 1 Part B) 4 hours (±1 hour) postdose (Section 9.2.2, Table 9).
- Dispense study treatment (ASTX029), provide instruction for self-administration as needed, and instruct subject to, on dosing days when there is a scheduled visit, refrain from ingesting the study drug until after being are on-site at the study clinic and the predose study procedures have been performed.
- Review dosing diary to assess dosing compliance.

9.4.11.7. Cycle 2 – Week 3 – Day 15

Week 3 is a dosing week in Regimen 1 (only): consecutive QD oral doses of study treatment will be administered (or self-administered) on Days 15 to 21.

For subjects receiving Regimen 1 treatment (before administration of study treatment) (note: hematology and serum chemistry tests may be performed on the day before the visit if more convenient):

- Perform symptom-directed PE (Section 9.4.1).
- Record vital signs (Section 9.4.2).
- Evaluate ECOG performance status (Appendix 1).
- Record AEs and concomitant medications.
- Collect blood samples for hematology and serum chemistry laboratory tests (Table 10).

Subject receiving Regimen 1 treatment ingests study treatment while at the clinic.

After administration of study treatment for subjects receiving Regimen 1 treatment:

- Record AEs and concomitant medications.
- Dispense study treatment (ASTX029), provide instruction for self-administration as needed, and instruct subject to, on dosing days when there is a scheduled visit, refrain from ingesting the study drug until after being are on-site at the study clinic and the predose study procedures have been performed.
- Review dosing diary to assess dosing compliance.

For subjects receiving Regimen 2 treatment (note: hematology and serum chemistry tests may be performed on the day before the visit if more convenient):

- Perform symptom-directed PE (Section 9.4.1).
- Record vital signs (Section 9.4.2).
- Evaluate ECOG performance status (Appendix 1).
- Record AEs and concomitant medications.
- Collect blood samples for hematology and serum chemistry laboratory tests (Table 10).

9.4.11.8. Cycle 2 End of Cycle (before Cycle 3 Day 1)

• Assess subject's disease by CT or MRI scan (or other appropriate disease evaluation method, including tumor marker measurement, as applicable).

9.4.11.9. Cycles 3 Through 6 – Week 1 – Day 1

Week 1 is a dosing week in both Regimens 1 and 2: consecutive QD oral doses of study treatment will be administered (or self-administered) on Days 1 to 7.

Before administration of study treatment (note: hematology, serum chemistry, coagulation, and urinalysis tests may be performed on the day before the visits and the pregnancy tests may be performed within 24 hours before administration of study treatment Cycles 3 through 6 if more convenient):

- Perform symptom-directed PE (Section 9.4.1).
- Record subject's weight.
- Record vital signs (Section 9.4.2).
- Evaluate ECOG performance status (Appendix 1).
- Perform predose 12-lead ECG in triplicate (Section 9.4.4).
- Record AEs and concomitant medications.
- Collect blood samples for hematology, coagulation, and serum chemistry laboratory tests; collect urine sample for urinalysis (Table 10).
- Perform serum or urine pregnancy test for women of child-bearing potential only.
- Collect predose blood sample for ctDNA (Section 9.2.2, Table 8).

Before administration of study treatment for subjects in Phase 2:

• Collect predose blood sample for PK analysis for Cycle 3 only (Section 9.2.1, Table 6 and Table 7).

Subject ingests study treatment while at the clinic.

After administration of study treatment:

- Record AEs and concomitant medications.
- Review dosing diary to assess dosing compliance.
- Dispense study treatment (ASTX029), provide instruction for self-administration as needed, and instruct subject to, on dosing days when there is a scheduled visit, refrain from ingesting the study drug until after being are on-site at the study clinic and the predose study procedures have been performed.
- Provide a dosing diary to the subject and instructions for how to enter dosing information.

After administration of study treatment for subjects in Phase 2:

• Collect postdose blood samples for PK analysis for Cycle 3 only (Section 9.2.1, Table 6 and Table 7).

9.4.11.10. Cycles 3 Through 6 – Week 2 – Day 8

Week 2 is a dosing week in both Regimens 1 and 2: consecutive QD oral doses of study treatment will be administered (or self-administered) on Days 8 to 14.

9.4.11.11. Cycle 3 Through 6 – Week 3 – Day 15

Week 3 is a dosing week in Regimen 1 (only): consecutive QD oral doses of study treatment will be administered (or self-administered) on Days 15 to 21.

9.4.11.12. End of Cycle 4 and at End of Every 4 Cycles (±1 Cycle) After Cycle 4 (Before Day 1 of Cycle 5 and Before Day 1 of Every 4 Cycles [±1 Cycle] After Cycle 5)

• Assess subject's disease by CT or MRI scan (or other appropriate disease evaluation method, including tumor marker measurement, as applicable).

9.4.12. Cycle 7 and Subsequent Cycles

After Cycle 6, the specific visit schedule and assessments are at the investigator's discretion; at a minimum, information should be collected regarding concomitant medications, AEs, dosing compliance, and, at least once a month, pregnancy tests. Continue to collect efficacy and response assessments, in the manner described in the protocol, until disease progression (for response assessment) or death (for survival assessment), or the subject withdraws consent.

9.4.13. Treatment Termination Visit

This visit should occur within 7 days after the last study treatment or within 3 days before starting new cancer treatment and before the 30-day Safety Follow-up visit. (Note: hematology, serum chemistry, coagulation, urinalysis, and pregnancy tests may be performed on the day before the visit if more convenient.) If a subject discontinues study treatment at a scheduled visit, the assessments at that visit can be used to fulfill the Tx Term visit requirements.

The visit should occur when a subject permanently discontinues study treatment, regardless of whether or not the subject plans to continue participating in the study, for long term follow up of health status (unless consent to continue study participation is withdrawn by the subject).

- Perform symptom-directed PE (Section 9.4.1).
- Record vital signs (Section 9.4.2).
- Evaluate ECOG performance status (Appendix 1).
- Perform 12-lead ECG in triplicate (Section 9.4.4).
- Perform ECHO or MUGA scan.
- Record AEs and concomitant medications.
- Collect blood samples for hematology, coagulation, and serum chemistry laboratory tests; collect urine sample for urinalysis (Table 10).
- Perform serum or urine pregnancy test for women of child-bearing potential only.
- Collect blood sample for ctDNA (Section 9.2.2, Table 8).
- Review dosing diary to assess dosing compliance.
- If the last disease assessment was >12 weeks prior to study treatment withdrawal and disease progression had not been documented, assess subject's disease by CT or MRI

scan (or other appropriate disease evaluation method, including tumor marker measurement, as applicable).

9.4.14. **30-day Safety Follow-up Visit**

This visit must occur 30 (\pm 5) days after the last dose of study treatment or within 3 days before starting a new cancer treatment.

- Perform symptom-directed PE (Section 9.4.1).
- Record vital signs (Section 9.4.2).
- Evaluate ECOG performance status (Appendix 1).
- Record AEs and concomitant medications.

9.4.15. Long-Term Follow-up of Health Status

For subjects who remain on study, beginning 3 months after the discontinuation of study treatment, the subject's health status will be collected by telephone every 3 months until death, or the subject withdraws consent, or until the end of the study, whichever occurs first. The following health information will be collected and recorded in the source documents and eCRF:

- Survival information.
- Date of disease progression if subject did not have disease progression at the time they discontinued study treatment.

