The ORR, PFS, and DOR endpoints will be based on the investigator's assessment of target and non-target lesions according to RECIST v1.1; computed tomography (CT) or magnetic resonance imaging (MRI) scans (or other appropriate disease evaluation method, including tumor marker measurement, as applicable) will be performed at baseline and every 2 cycles for the first 4 cycles, and then every 4 cycles (± 1 cycle) thereafter until clinical and/or radiographic disease progression, death, or the subject withdraws consent. Subjects will be followed for OS.

Pharmacokinetics Assessments:

Serial blood sampling (up to 24 hours postdose) on the following study days will allow assessment of systemic exposures of ASTX029:

- Phase 1: Cycle 1 Day 1 (C1D1), Cycle 1 Day 2 (C1D2), Cycle 2 Day 1 (C2D1), and Cycle 2 Day 2 (C2D2) for Regimen 1 and C1D1, C1D2, Cycle 1 Day 14 (C1D14), and Cycle 1 Day 15 (C1D15) for Regimen 2.
- Phase 2: C1D1, C1D2, C2D1, and Cycle 3 Day 1 (C3D1) for Regimen 1 and C1D1, C1D2, C1D14, C1D15, and C3D1 for Regimen 2.

At specified study visits, blood samples, including predose and trough samples, will be collected. Additional ad hoc blood sample(s) may be collected per investigator discretion, for PK measurement at any time, including after the last dose, if there is a suspected safety issue. Plasma drug concentration data will be used to determine the PK parameters listed under Secondary Endpoints in all subjects during Cycle 1 and Cycle 2 if data are evaluable.

Pharmacodynamic and Biomarker Assessments:

The pharmacodynamic modulation and target engagement will be explored in fresh tumor tissue biopsies (when available). Identification and monitoring of potential biomarkers (DNA, RNA, and protein) of ASTX029 activity will be assessed in ctDNA, blood, and tumor tissue biopsies.

Safety Assessments:

At each study visit, safety will be monitored by recording AEs, serious adverse events (SAEs), DLTs, and concomitant medications; additional safety assessments at selected visits include complete or symptom-directed physical examinations (PEs), weight and height, vital signs, Eastern Cooperative Oncology Group (ECOG) performance status, 12-lead ECGs, ECHO/MUGA scans, and clinical laboratory tests (hematology, coagulation, serum chemistry, and urinalysis). All AEs will be graded by National Cancer Institute (NCI) Common Terminology Criteria for Adverse Events (CTCAE) v4.03.

Sample Size and Statistical Analyses: Sample Size Calculation:

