Recommended Phase 2 Dose

The RP2D is defined as the dose that the DSRC agree shows adequate safety, PK, pharmacodynamic, and/or biological or clinical activity to warrant further investigation in the Phase 2 part of this study. The RP2D decision by the DSRC will be based on all available PK, biomarker, safety, and preliminary clinical activity data from all cycles, including potential for late or cumulative toxicity from Phase 1 Parts A and B. The RP2D could be the same or lower than the RDE.

Based on the data presented in Section 1.3.3, the DSRC determined the RP2D to be 200 mg administered orally daily, continuously, in 21-day cycles under fasting conditions.

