9. STUDY ASSESSMENTS AND PROCEDURES

9.1. Preliminary Clinical Activity Assessments

Measurable disease according to RECIST v1.1 (Appendix 3) will be assessed using CT or MRI scans at baseline (screening), every 2 cycles (\pm 7 days) for the first 4 cycles, and then every 4 cycles (\pm 1 cycle) thereafter until clinical and/or radiographic disease progression, death, or the subject withdraws consent. Tumor markers (if applicable) should be measured at the same time points as the time points for radiological assessments.

For subjects whose disease is not measurable using RECIST v1.1, disease status must be reliably and consistently followed using another generally acceptable method.

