- ^u See Table 8 for the ctDNA sample collection schedule. On dosing days, predose samples are to be collected within 60 minutes prior to administration of study treatment.
- ^v If archived tumor tissue (FFPE) is available, it will be requested for use in this study during screening. In addition, collection of fresh tumor biopsies is encouraged (optional) in Phase 1 Part A and Phase 2 and mandatory in Phase 1 Part B of the study during screening and on C2D8 (±1 day), 4 hours (±1 hour) postdose. See Table 9 for the biopsy collection schedule.
- ^w CT or MRI scan (or other appropriate disease evaluation method, including tumor marker measurement, as applicable) will be performed at screening, at the end of every 2 cycles (±7 days) for the first 4 cycles, and then every 4 cycles (±1 cycle) thereafter until clinical and/or radiographic disease progression, or death, or the subject withdraws consent, whichever occurs first (Section 9.1, Section 9.4.8). If the last assessment was >12 weeks prior to study treatment withdrawal and disease progression had not been documented, a disease assessment should be obtained at the Tx Term visit.
- ^x Beginning 3 months after discontinuation of treatment, subjects will be contacted by telephone for collection of health status information every 3 months until death, the subject withdraws consent, or end of study, whichever occurs first (Section 9.4.15).

Table 12: Schedule of Events Regimen 2 – Intermittent (Days 1 Through 14) Dosing

Cycle (21 Days) ^a				1				2		≥3 ª	Tx Term ^b	30-day Safety FU ^c	Long- term FU
Cycle Day ^d			2	8	14	15	1	8	15	1			
Study treatment dispensation		х		x			x	x		х			
Dosing compliance information				x	x			x		х	x		
Procedures	Screening ^f												
Informed consent	X												
Medical history	X												
Investigator's confirmation of eligibility	х	x											
PE/symptom-directed PE ^g	х	x		x	x		x	x	x	х	x	х	
Height	x												
Weight	x	x					x			X			
Vital signs ^h	X	x	x	x	x	x	x	x	x	x	x	x	
ECOG performance status	x	x		x	x		x	x	x	х	x	x	
12-lead ECG ⁱ	x	x	x	x	x	x	x			х	x		
ECHO or MUGA scan	X	Repeat every 2 cycles for the first 4 cycles and then every 4 cycles thereafter (±7 days)				x							
Ophthalmic examination ^j	X												
Concomitant medications/AEsk	X	x	x	x	x	x	x	x	x	х	x	х	
Randomization (if applicable), enrollment	X												
Laboratory Assessments													
Hematology ^{l,m}	X	x		x	x		x	x	x	х	X		
Coagulation ^{m,n}	x	x					x			х	x		

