In this study, tumor measurement will be conducted at the end of every 2 cycles (\pm 7 days) for the first 4 cycles and then every 4 cycles (\pm 1 cycle) thereafter until clinical and/or radiographic disease progression, or death, or the subject withdraws consent. Scan dates should not be adjusted or rescheduled due to dose interruption of any type.

Baseline tumor assessments must be performed within 3 weeks (21 days) prior to the first dose of treatment.

All efforts should be made to ensure consistency between the baseline measurements and all subsequent measurements in reference to utilization of scanning method, equipment, technique (including slice thickness and field of view), and radiographic interpreter.

The radiographic evaluation must include CT or MRI scanning of the known sites of involvement, as well as the chest, abdomen, and pelvis if they are not the primary target. Any additional suspected sites of disease should also be imaged. All evaluations should meet the standard of care for imaging of lesions in the respective organ(s) and should conform to the image acquisition guidelines according to institutional standards.

All target and nontarget sites are evaluated at each time point of tumor assessment.

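### After treatment stops without progression, scans are required in general terms but no off-treatment visit schedules them, and the SAP's DOR censoring can credit unscanned responders with response time nobody observed

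*Protocol*

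**What the plan says.** **Scans continue.** Protocol 9.1 sets scans every 2 cycles for the first 4 cycles, then every 4 cycles, "thereafter until clinical and/or radiographic disease progression, death, or the subject withdraws consent". Table 11 footnote w and Table 12 footnote v say the same: "until clinical and/or radiographic disease progression, or death, or the subject withdraws consent, whichever occurs first". Appendix 3 repeats the rule and asks for every effort to document objective progression after treatment ends. None of these makes stopping treatment an end point for scanning.

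**Visits after stopping.** Section 9.4.13 asks for a scan at Treatment Termination only if the last one was more than 12 weeks earlier and progression is undocumented. The 30-day visit (9.4.14) lists no scan. Long-term follow-up (9.4.15) is a telephone contact every 3 months that records survival and "Date of disease progression if subject did not have disease progression at the time they discontinued study treatment". Section 5.4.1 keeps subjects in follow-up but only encourages investigators to assess them according to the protocol. Table 13, to which 5.4.4 sends investigators for all patients until study completion, ends scans at radiologic progression or new anticancer therapy, which is a different stopping rule.

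**Analysis.** The Synopsis states: "The ORR, PFS, and DOR endpoints will be based on the investigator's assessment of target and non-target lesions according to RECIST v1.1". SAP 7.5.3 describes progression through its RECIST Table 1 and censors PFS at the last disease assessment. Protocol 11.6.4 ends DOR, for responders without relapse or death, at the last disease assessment. SAP 7.5.2 censors it at study termination. SAP 1.0 says the SAP supersedes the protocol's analysis plan, and SAP 7.9 does not list this change.

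**Dose interruption.** Appendix 3 is explicit: "Scan dates should not be adjusted or rescheduled due to dose interruption of any type". Sections 9.4.11.8 and 9.4.11.12 place scans by cycle start, for example "Before Day 1 of Cycle 5 and Before Day 1 of Every 4 Cycles".

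**The concern.** A site working from the visit procedures would order no scan after Treatment Termination for a subject who stopped, say, for toxicity. A site working from 9.1 would keep scanning. Progression would then be established by lesion measurement for some subjects and by a date given at a telephone contact for others. The difference would follow the reason for stopping, so it need not be random.

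The SAP has no rule for a progression date without a scan, and none for missed scans or new therapy. For DOR the stated rule makes things worse: with censoring at study termination, an unscanned responder counts as still responding up to that date. Scans that were not taken cannot be recovered at analysis.

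**Working it through.** The plan gives no figure to reproduce here. The check is calendar arithmetic plus a comparison of the rules.

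**1. Nominal scan calendar.** Cycles are 21 days. Scans fall at 2 × 21 = day 42 (week 6), 4 × 21 = day 84 (week 12), 84 + 84 = day 168 (week 24) and 168 + 84 = day 252 (week 36). The window is ±7 days for the first two (days 35–49 and 77–91). Later scans are 84 ± 21 days apart (63–105 days).

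**2. How often the termination scan is triggered.** It needs a last scan more than 12 weeks (84 days) old. The longest nominal gap is exactly 84 days, so on the nominal calendar it is never triggered. It arises only when a scan is late within its window (gap up to 105 days) or missed.

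**3. PFS, worked case.** Last scan week 6, treatment stopped at week 10 without progression, true progression at week 11. At stopping the last scan is 10 − 6 = 4 weeks old, so no termination scan is due.
- Scans continue under 9.1: event at the week-12 scan.
- Visit procedures only, telephone date counted: event dated between week 11 and the first call, at about 10 + 13 = week 23.
- Visit procedures only, telephone date not counted: censored at week 6.

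**4. DOR, worked case.** First response week 6, still responding at week 12, stopped at week 14, no later scan and no progression recorded. The termination scan is not due (14 − 12 = 2 weeks). The study termination date is my assumption; I use weeks 24 and 36.
- Protocol 11.6.4: censored at 12 − 6 = 6 weeks.
- SAP 7.5.2: censored at 24 − 6 = 18 weeks, or 36 − 6 = 30 weeks.

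The excess is study termination minus last scan: 12 or 24 weeks here, growing with follow-up.

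**5. Illustration for PFS.** A simulation of 20,000 subjects per setting used assumptions that are not in the documents: exponential PFS with median 2, 4 or 6 months; 10% or 30% stopping for reasons other than progression, independently of it; calls every 13 weeks after stopping. Between 11% and 39% of subjects were off treatment before the scan that would have shown progression.
- Progression dated at the call: 24-week PFS rose by 1 to 9 points (0.526 to 0.536 at the low end, 0.143 to 0.236 at the high end).
- Telephone dates not counted, censored at the last scan: 24-week PFS moved by less than 1 point, but only because stopping was assumed unrelated to progression.
- The median was unchanged in most settings. It moved from 12.0 to 14.4 weeks in one (call date used) and from 36.0 to 30.1 weeks in another (true date reported by telephone).

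**6. Dose interruption.** If a scan followed a delayed Cycle 3 start, a 7-day delay would give day 49 (inside the window), 14 days would give day 56 and 20 days would give day 62 (both outside). But a scan kept on day 42 still precedes a delayed Cycle 3 Day 1, so it satisfies both 9.4.11.8 and Appendix 3.

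**The case against.** The best reply is that this is silence, not contradiction. No passage says scans end when treatment stops. Sections 9.1 and 9.4.12, the table footnotes and Appendix 3 all point to continued scanning, and 9.4.15 lists data items without saying that the progression date is patient-reported or lacks imaging. That stands as far as it goes, and a reader who infers that the protocol forbids or replaces off-treatment scans goes beyond the text. It does not remove the gap: no visit after Treatment Termination lists a scan, 5.4.1 only encourages assessment, and Table 13 stops scans on a different rule. I do not rely on the long-term follow-up column of Tables 11 and 12, because the response row is one merged entry whose span is unclear.

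The second reply is that SAP 7.5.3 already ties progression to RECIST Table 1, so a telephone-only date would not count for PFS. That is the more natural reading, and it weakens any inference that such dates will enter PFS. The SAP does not say so, however, and this reply does not touch the DOR censoring date.

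A reader might also infer that dose holds delay scans and so lengthen PFS. The documents do not support that. Appendix 3 settles the matter and states its schedule in the same cycles as 9.4.11.8 and 9.4.11.12. Nothing says a hold restarts the cycle count, and after Cycle 4 the ±1-cycle window already covers 21 days. Nor does Section 7.5 leave a 21-day hold free of approval: restarting after an interruption of 21 days or more needs the medical monitor's agreement.

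**Conclusion.** The point holds for subjects who stop treatment without RECIST progression. Scanning is required in general terms, no off-treatment visit carries it out, and the SAP leaves unscanned progression dates undefined. The firmest part is DOR: the governing SAP rule censors at study termination, contrary to Protocol 11.6.4, and adds the whole interval since the last scan to an unscanned responder's censored duration.

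The size for a cohort cannot be derived, because the documents give no PFS or discontinuation assumption; the simulated shifts only show what is possible. PFS and DOR are secondary and descriptive, with no comparison planned, so this is a correction worth making rather than a threat to the Phase 2 primary result. I make no claim about ORR. Appendix 3 takes best response up to the end of treatment, while SAP 7.5.1 words it as all post-baseline assessments. The dose-interruption point is minor.

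**What to change.** 1. **Protocol.** Reconcile 5.4.1, 9.4.13 to 9.4.15 and Table 13 with 9.1, stating that the 9.1 scans continue for subjects who stop without RECIST progression. Say explicitly what applies after clinical progression only, since 9.1 as written ends scanning there, and after new anticancer therapy, where Table 13 differs.
2. **SAP 7.5.2 and 7.5.3.** Count progression as an event only when a RECIST assessment supports it; death remains an event. Otherwise censor PFS and DOR at the last disease assessment, replacing the study-termination censoring of DOR. Count telephone-only progression dates as events in one sensitivity analysis. If any departure from Protocol 11.6.4 remains, list it in SAP 7.9.
3. **Minor.** In 9.4.11.8 and 9.4.11.12, cross-refer to the Appendix 3 sentence that scan dates do not move for dose interruption.

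The cost is a protocol clarification and a few lines of SAP text. For subjects who stop without any progression, 9.1 already requires the scans; continuing them after clinical progression alone would be an addition. The downside is somewhat more censoring, which may be informative if subjects who leave scanning are those about to progress. The sensitivity analysis shows how much that matters.
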